 Impact of the intervention on overall healthcare costs Predicted long- term health impact and cost- effectiveness of the intervention from the health system (payer) perspective 	 We will measure the cost of delivering the intervention using micro-cost accounting methods and the incremental medical care costs attributable to the intervention, defined from the health system perspective, measured using insurance claims incurred in the median 12-month pre- and post- index date periods by participants with an affiliated HealthPartners insurance plan in each study group. We will use a cardiovascular disease microsimulation model to predict the impact of the intervention on health outcomes and its cost- affective and defined from the 	 If the intervention is found to be effective, the cost of delivering the intervention and its incremental effect on medical care utilization will be important outcomes to informing dissemination and implementation to other systems and settings. A full measurement of the value of the intervention cannot be observed during the study period, but validated microsimulation methods can be used to estimate the full impact of the intervention on preventing or delaying incidence of disease and in averting future medical care costs—both of which will be important to inform the
	effectiveness, defined from the health system perspective, over up to a 30-year prospective time horizon.	translation and adoption of the intervention, if found to be effective.
Tertiary/Exploratory	health system perspective, over up to	translation and adoption of the

	OBJECTIVES		ENDPOINTS	JUSTIFICATION FOR ENDPOINTS
	What are we			
			How are we measuring it?	
	measuring			
1.	The impact of the	1.	We will assess reduction in 10-	The CDS assesses and prioritizes CV
	intervention on		year CV risk measured at each	risks factors according to the
	10-year CV risk		encounter	percentage of 10-year CV risk that
2.	Survey assessed	2.	We will conduct phone surveys	can be reduced if actions are taken
	patient reported		on a random sample of up to	to address the risk factor.
	adherence		1400 eligible patients	
З.	Patient and		approximately 2-4 weeks after an	Provider and patient experience and
	provider		index visit and subsequently ~6	satisfaction information provide end-
	experience and		months later (after a phone	user opinions of the intervention
	satisfaction		outreach has occurred)	which helps to assess impact and

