9 STATISTICAL CONSIDERATIONS

9.1 STATISTICAL HYPOTHESES

• Primary Efficacy Endpoint(s):

For patients 18 to 75 years old not at goal for BP, A1C, or statin use and with medication nonadherence, those randomly assigned to the ReachOut Adherence Intervention will have improved adherence and clinical outcomes compared to those randomly assigned to control.

Hypothesis 1.1 Relative to those assigned to control, eligible adults with uncontrolled BP and baseline nonadherence to one or more BP medications who are assigned to intervention will be more likely to achieve (a) an e-PDC \geq 80% for all BP medications and (b) a reduction in systolic BP in the 12-month period after the index visit.

Hypothesis 1.2 Relative to those assigned to control, eligible adults with diabetes and A1C \geq 8% and baseline nonadherence to a non-insulin glycemic medication who are assigned to intervention will be more likely to achieve (a) e-PDC \geq 80% for all non-insulin glycemic medications and (b) a reduction in A1C values in the 12-month period after the index visit.

Hypothesis 1.3 Relative to those assigned to control, eligible adults with inadequately managed lipid disorders with baseline non-adherence to a statin who are assigned to intervention will be more likely to achieve an e-PDC \geq 80% for a statin in the 12-month period after the index visit.

• Secondary Efficacy Endpoint(s):

Assess the cost and cost-effectiveness of the ReachOut Adherence Intervention from the health system (payer) perspective through empirical analysis and microsimulation modeling of patient utilization and disease outcomes.

Hypothesis 2.1: Relative to those who are assigned to control, eligible study subjects who are assigned to intervention will have significantly higher overall health care costs in the 12-month period following the index visit, after controlling for demographics and baseline clinical risk factors.

Hypothesis 2.2: Relative to those who are assigned to control, eligible study subjects who are assigned to intervention will have significantly lower overall resource use and fewer major CV and diabetes-related events in a 30-year post-intervention simulated analysis using cost-effectiveness microsimulation modeling methods.

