9.3 POPULATIONS FOR ANALYSES

The **analysis population** is limited to subjects who meet intervention eligibility requirements at an index visit. We will use data from the Wizard algorithm runs outside the encounter at 6 and 12 months post-index visit to analyze the impact of the intervention on adherence (e-PDC) and clinical outcomes (A1C, BP, statin use). The cost analysis is limited to the subset of these patients who have HealthPartners insurance for at least 11 of 12 months after the index visit.

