9.4.3 ANALYSIS OF THE SECONDARY ENDPOINT(S)

Definition of Health Care Costs: Costs for this analysis include intervention costs and incremental medical care costs attributable to the intervention, defined from the health system perspective. Intervention costs include implementation, incentives to maintain high use rates, maintenance, and training but exclude research, development, and measurement costs.¹¹⁶ Standard micro-cost accounting methods and nationally representative pricing of inputs will be used to measure the cost of the intervention. We include clinic payments to reimburse pharmacist time and resources for conducting active outreach. Medical care costs include the cost of all prescribed medications and clinic services—including laboratory, MTM pharmacist, educator, and physician services—incurred in the 12-month preand post-index date periods by participants in each study group, as indicated by insurance claims and clinical encounter data. Emergency department visits and hospitalizations may be too infrequent in the study sample to accurately predict a population wide impact. To avoid substantially increasing variance without adding accuracy to the cost assessment, we will include emergency department and inpatient costs only if a significant difference in these is observed.

While market prices generally are a good estimate of the costs for medical services, the paid amount in this claims system is specific to HP at a particular time and may provide a biased view of costs between pre- and post-intervention periods. To address this, we will use Total Care Relative Resource Values[™]

(TCRRVs), which are a nationally standardized set of measures that have been endorsed by the National Quality Forum¹¹⁷ and are derived from Centers for Medicare and Medicaid Services (CMS) relative value units (RVUs). TCRRVs extend CMS RVU measures to include utilization categories, such as laboratory services and medications, which do not have CMS RVU weights¹¹⁸. Specifically, TCCRVs defined during the midpoint of patient accrual and follow-up (e.g., 2020) will be used to convert claims to represent U.S. dollars.

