Analytic Plan for Health care costs (12-month Utilization): Incremental medical costs will be estimated using standard health econometric methods. A generalized estimating equation (typically assuming a gamma distribution and log link function) will be used to estimate costs by study arm while controlling for demographics and baseline clinical risk factors.¹¹⁹⁻¹²¹ The marginal effect of being assigned to an intervention clinic will provide an estimate of the incremental medical cost associated with the ReachOut adherence intervention.

Definition of Long-term Cost and Health Outcomes: Health outcomes include incidence, morbidity, and mortality of CV disease (including myocardial infarction, stroke, congestive heart failure, and angina pectoris) and microvascular complications due to diabetes (including blindness, ulcer, first amputation with no previous ulcer, first amputation with previous ulcer, second amputation, and renal failure). Medical costs corresponding with the incidence and ongoing management of these conditions are based on nationally representative data derived from the Medical Expenditure Panel Survey.¹²²

Analytic Plan for Long-term Costs and Outcomes: The HealthPartners Institute ModelHealthTM: A cardiovascular disease (CVD) microsimulation model will be used to estimate long-term outcomes and cost-effectiveness from the health system perspective.¹²³ ModelHealth: CVD is an annual-cycle microsimulation model that, in its base configuration, is parameterized to estimate lifetime CV events and disease costs in persons representative of the U.S. population. The model has been previously used to conduct a decision analysis for the U.S. Preventive Services Task Force recommendation on aspirin and to evaluate improvements in hypertension, lipid, and lifestyle management.¹²⁴⁻¹²⁹

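### Emergency and inpatient costs enter the 12-month overall cost outcome (H2.1) only if an undefined significance test on the same data is positive, and the cost model ignores this step

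*Combined protocol and SAP*

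**What the plan says.** Section 3 lists as a secondary objective "Impact of the intervention on overall healthcare costs". The matching endpoint measures incremental medical care costs from insurance claims, with no exclusion of emergency department (ED) or inpatient care. Hypothesis 2.1 in section 9.1 says that intervention patients "will have significantly higher overall health care costs in the 12-month period following the index visit".

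Section 9.4.3 then defines the content more narrowly: "Medical care costs include the cost of all prescribed medications and clinic services". ED and inpatient costs are not in that list. The reason given is "Emergency department visits and hospitalizations may be too infrequent in the study sample to accurately predict a population wide impact". To avoid adding variance, the plan says "we will include emergency department and inpatient costs only if a significant difference in these is observed".

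For the analysis, the same section specifies a generalized estimating equation, typically gamma with log link, which "will be used to estimate costs by study arm while controlling for demographics and baseline clinical risk factors". It does not mention the inclusion step. Section 9.3 sets the population: "The cost analysis is limited to the subset of these patients who have HealthPartners insurance".

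**The concern.** The outcome is decided after looking at part of it, in the same patients. The plan does not state the test, its alpha, whether costs or events are compared, or whether ED and inpatient care are tested together or separately. Two analysts could follow the text and analyse different outcomes.

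If the test is not significant, any true ED/inpatient difference is set to zero, and the result is medication and clinic cost under the name of overall cost. If the test is significant, the difference that enters is exaggerated on average, because only large observed values get in. In neither case do the reported standard error and P value reflect the selection.

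Net cost is overstated if the intervention lowers ED and inpatient use, and understated if it raises that use. The documents do not establish which applies. Section 3 says that the cost results are meant to inform adoption by other systems, so the error would reach that decision.

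**Working it through.** **No figure to reproduce.** The plan gives no alpha, sample size, cost SD, effect size or power for H2.1. The check is therefore of how the written rule behaves under stated assumptions.

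**Does another section cure it?** The cost model in section 9.4.3 adjusts only for demographics and baseline risk factors. The sensitivity methods later in that section belong to the microsimulation and its cost-effectiveness ratios. No 12-month analysis is certain to include ED and inpatient costs.

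**Set-up (assumed).**
- A is the estimated arm difference in medication and clinic cost, with SE 1.
- B is the estimated arm difference in ED plus inpatient cost, with SE r. The documents do not give r; values 0.5, 1, 3 and 5 are shown.
- A and B are normal and independent.
- There is one joint pre-test on cost, |B/r| > 1.96. H2.1 is tested two-sided at 0.05.
- If the pre-test is significant, the estimate is A + B with SE √(1 + r²). Otherwise it is A with SE 1.

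**1. No true difference in either component.** The rejection rate is 0.95 × 0.05 + 0.05 × P(reject | pre-test significant). At r = 1 the conditional probability is 0.338, so the rate is 0.0475 + 0.0169 = 0.0644.

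| r | 0.5 | 1 | 3 | 5 |
|---|---|---|---|---|
| P(reject given pre-test significant) | 0.157 | 0.338 | 0.705 | 0.817 |
| Rejection rate of H2.1 | 5.5% | 6.4% | 8.3% | 8.8% |

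Other readings of the rule, over the same r:
- Correlation 0.5 between A and B: 6.0% to 8.4%.
- Pre-test on event counts (correlation 0.69 between count and cost statistics, assuming 10% hospitalised and exponential costs): 5.3% to 6.3%.
- Separate ED and inpatient pre-tests (ED SE 0.1 to 0.5 of the outpatient SE): 5.6% to 9.3%.

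A patient-level simulation with skewed costs and 300 or 1,000 patients per arm gave 5.1% to 5.5% at r about 0.4, 6.2% to 6.7% at r about 1, and 7.8% to 8.0% at r about 2.7. Full inclusion gave about 5%.

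**2. A true ED/inpatient difference of d standard errors.** With Z ~ N(d, 1) and pre-test power π = P(|Z| > 1.96), the mean share of the difference kept is

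[dπ + φ(1.96 − d) − φ(1.96 + d)] / d.

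The exaggeration when it is included is that share divided by π. At 10% power, d = 0.652 and the share kept is 0.34. So 66% is lost, and the exaggeration is 0.34 / 0.10 = 3.4. Neither quantity depends on r.

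| Pre-test power | 10% | 20% | 50% | 80% |
|---|---|---|---|---|
| d | 0.652 | 1.115 | 1.960 | 2.802 |
| Mean share lost | 66% | 55% | 30% | 10% |
| Exaggeration when included | 3.4 | 2.2 | 1.4 | 1.1 |

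**3. Coverage of nominal 95% intervals for total cost.**

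| Pre-test power | r = 0.5 | r = 1 | r = 3 | r = 5 |
|---|---|---|---|---|
| 10% | 93% | 89% | 52% | 16% |
| 20% | 92% | 82% | 24% | 17% |
| 50% | 89% | 73% | 48% | 48% |
| 80% | 91% | 81% | 78% | 78% |

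With a pre-test on counts, coverage over these powers is 92–94%, 84–92%, 47–77% and 20–77% at the four values of r.

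**The case against.** The rule is written in advance and has a reason. Where ED and inpatient differences are truly negligible, it does what it is meant to do. With no true difference, the root mean squared error for total cost is 1.13 under the rule against 1.41 with full inclusion at r = 1, and 1.87 against 3.16 at r = 3. At 10% pre-test power it is still lower (1.32 against 1.41 at r = 1). This stands, but the advantage has reversed by 20% power (1.56 against 1.41). A smaller mean squared error also does not make the stated P value or interval valid. A wish for less variance supports a definition fixed in advance, not a significance test. If events are too rare for accuracy, the pre-test has little power to find a real difference.

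Much of the under-coverage at low power comes from leaving the costs out, not from the selection as such. At 10% power, always excluding them covers total cost in 94%, 90%, 50% and 10% of trials across the four values of r, close to the first row of the coverage table. This is correct. The target is still total cost, because sections 3 and 9.1 name overall cost.

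The calculation uses additive normal differences, not the planned adjusted gamma model, and the patient-level check covers only the no-difference case. The direction does not hinge on that choice, but the sizes might.

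**Conclusion.** The concern holds. As written, the rule gives a biased 12-month cost estimate whenever a true ED/inpatient difference exists, and intervals that are too narrow. With no such difference the estimate is unbiased and the test is mildly anti-conservative. The sizes rest on assumed r, pre-test power, independence and two-sided 0.05 tests, because the documents supply none of these for cost.

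The reach is limited to the H2.1 estimate in the insured subset. No primary hypothesis is affected. The 30-year model is not clearly affected: its disease costs "are based on nationally representative data derived from the Medical Expenditure Panel Survey", and it is driven by risk factors and medication use. The change should be made, but this does not threaten the main conclusions of the trial.

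**What to change.** Delete the conditional sentence in section 9.4.3 and rewrite the definition so that medical care costs for H2.1 always include ED and inpatient costs. Add cost without these components as a pre-specified, labelled sensitivity analysis. The sentence about infrequent events can stay as its rationale.

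An alternative also removes the selection: always exclude these costs, rename the outcome as outpatient and medication cost in sections 3, 9.1 and 9.4.3, and always report the ED/inpatient difference separately with its confidence interval.

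The work is a text edit and one extra analysis. No new data are needed: the plan's own pre-test already requires this information, costs come from insurance claims, and section 10.1.9.1 lists inpatient encounters among the extracted elements.

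The price of always including is a wider interval than for outpatient cost alone, by √(1 + r²) if the components are independent: 1.1, 1.4, 3.2 and 5.1 times at r = 0.5, 1, 3 and 5. With correlation 0.5 the factor at r = 1 is √(1 + 1 + 2 × 0.5) = 1.7. That width reflects real uncertainty about total cost.

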4.2 SCIENTIFIC RATIONALE FOR STUDY DESIGN

This trial was originally conceived and approved as a clinic cluster randomized trial of control (usual care) versus intervention. However, the intervention was suspended in March 2020 after one week of implementation due to COVID-19 pandemic response that resulted in loss of the separation of treatment groups. There were clinic closures, decreased office visits, and increase in telehealth care. To address concerns related to patient crossover from intervention to control settings (and vice versa) in the ongoing COVID-19 era, the study was transitioned to a patient level randomization that was conducted using a computerized allocation by the CDS at the time of an index visit within any of the 28 study clinics. The main advantage to the patient level randomization is that no matter what happens with clinics closing and opening, provider moving between clinics, and where video encounters take place, the study subjects consistently receive the ReachOut intervention or usual care without crossover. Additionally study power increases with the patient-level design compared to a clinicrandomized design. The disadvantage to the patient level randomization design, and why it wasn't the initial choice when the grant was originally funded, is concern over clinician contamination due to a potential learning effect from the intervention that translates to control patients. However, the net effect of this contamination would be a reduction in the intervention effect which would not undermine conclusions if the intervention is found to be effective. Given how the clinical setting changed abruptly and unexpectedly due to the COVID-19 pandemic, the advantages of a patient-level study design were determined to outweigh the disadvantages and be the most appropriate way to complete the study and test the hypotheses.

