6.3 MEASURES TO MINIMIZE BIAS: RANDOMIZATION

Patients are randomly allocated 1:1 through a computer-generated program to either control or intervention. Contamination across intervention arms is unlikely because all patients receive CDS interventions based on their arm assignment. All patients assigned to the study arms are analyzed based on their arm assignment.

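### The health care cost model gives no role to pre-index cost, which the trial collects, and so gives up precision

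*Combined protocol and SAP*

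**What the plan says.** **Model.** In section 9.4.3 (analytic plan for health care costs), a generalized estimating equation, typically gamma with a log link, "will be used to estimate costs by study arm while controlling for demographics and baseline clinical risk factors". H2.1 in section 9.1 has the same outcome window and covariates: it concerns "overall health care costs in the 12-month period following the index visit, after controlling for demographics and baseline clinical risk factors".

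**Data.** Section 9.4.3 defines medical care costs as those "incurred in the 12-month preand post-index date periods by participants in each study group". The endpoint table in section 3 agrees: incremental costs are "measured using insurance claims incurred in the median 12-month pre- and post- index date periods". Section 9.4.3 also adopts standardized TCRRVs because paid amounts could distort a comparison of the two periods, so some use of the pre-index data is evidently intended. No sentence says what use.

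**Coverage.** Section 9.3 limits the cost analysis to patients insured for at least 11 of the 12 post-index months and asks for no pre-index coverage. Section 5.2, exclusion 4, uses 30 continuous days in the year before or the year after index.

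**Name of the effect.** Section 9.4.3 continues: "The marginal effect of being assigned to an intervention clinic will provide an estimate of the incremental medical cost". Section 4.2 says that "the study was transitioned to a patient level randomization", and section 6.3 that "Patients are randomly allocated 1:1 through a computer-generated program to either control or intervention".

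**The concern.** Costs are skewed, the cost analysis is confined to an insured subset, and the plan gives no sample size, SD or power for H2.1. Section 9.4.3 is itself worried about variance: it holds emergency and inpatient costs out unless they differ significantly between arms. In that setting a pre-treatment measurement of the outcome is an obvious covariate, and the plan collects one without giving it a place in the model.

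At stake is the width of the interval around the incremental medical cost. There is also a specification gap. With cost held for both periods and no stated role for the first, the analyst could compare post-index cost alone, compare changes, or adjust for baseline, and these differ in precision.

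**Working it through.** **1. Is pre-index cost in the model under any written rule?** The covariate lists in sections 9.1 and 9.4.3 do not include it. The SBP/A1C model in section 9.4.2 writes out time and arm-by-time terms; the cost model has neither, and H2.1 sets a post-index outcome. As written, the model is post-index cost on arm plus demographic and clinical covariates.

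**2. Reference check on a figure the plan does give.** The plan states no cost figure to reproduce. Its SBP calculation (section 9.2) does use a pre/post correlation: difference 3 mmHg, SD 15.8, ρ = 0.5, 80% power, two-sided α = 0.05.

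- Change score: SD = 15.8 × √(2(1 − 0.5)) = 15.8. Patients per arm = 2 × (1.960 + 0.842)² × 15.8² / 3² ≈ 435.4, rounded up to 436, so N = 872. This matches the plan.
- Baseline-adjusted: multiply by 1 − 0.5² = 0.75. Per arm 327, so N = 654, which is 25% fewer.

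**3. The same factor applied to cost.** Let ρ be the correlation between pre- and post-index cost left after the planned covariates. It is not in the documents; 0.3 to 0.7 is assumed. On a linear scale adjustment multiplies the variance of the arm effect by 1 − ρ². Equal precision without it needs 1/(1 − ρ²) times the patients. An analysis with 80% power unadjusted (illustrative only) would have power Φ(2.802/√(1 − ρ²) − 1.960).

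| ρ (assumed) | Variance factor | Variance cut | SE ratio | Patients needed without adjustment | Power, from 80% |
|---|---|---|---|---|---|
| 0.3 | 0.91 | 9% | 0.954 | × 1.10 | 83.6% |
| 0.5 | 0.75 | 25% | 0.866 | × 1.33 | 89.9% |
| 0.7 | 0.51 | 49% | 0.714 | × 1.96 | 97.5% |

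**4. Check on the planned scale.** Log-normal costs were simulated with no arm effect and fitted with a gamma/log-link model (800 patients, 600 replicates, log-SD of 1, all assumed). The fit was run with and without the baseline term.

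| Log-scale correlation | Mean estimate without / with | Empirical SE without / with | SE ratio |
|---|---|---|---|
| 0.3 | −0.0028 / −0.0010 | 0.0906 / 0.0844 | 0.93 |
| 0.5 | −0.0004 / −0.0027 | 0.0913 / 0.0738 | 0.81 |
| 0.7 | −0.0059 / −0.0017 | 0.0928 / 0.0598 | 0.64 |

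The gain is in the same direction as the linear formula and somewhat larger. Every mean is within two Monte Carlo standard errors of zero (the largest, −0.0059, against 0.0928/√600 ≈ 0.0038), so neither version is biased.

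**5. Will the covariate be complete?** Not for everyone. Section 9.3 requires only post-index coverage. Even the stricter reading of section 5.2 would secure only 30 days before index. Some patients will have partial or no pre-index claims, and for them the gain is smaller than tabulated.

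**The case against.** The best defence is that the plan is silent rather than deficient. A generalized estimating equation is a method for correlated observations, costs are defined over both periods, and the TCRRV rationale speaks of comparing them. A repeated-measures pre/post model may be what was meant. In that case pre-index cost is already on the outcome side, and adding it as a covariate would use it twice.

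Part of this stands: the plan should say which model it means. But no time or arm-by-time term is written and H2.1 names only post-index cost, so the pre/post model is a conjecture. Nor would it remove the point. With equal variances a change comparison has relative variance 2(1 − ρ), so baseline adjustment multiplies it by (1 − ρ²)/(2(1 − ρ)) = (1 + ρ)/2. At ρ = 0.3, 0.5 and 0.7 that is 0.65, 0.75 and 0.85, still a saving of 35%, 25% and 15%.

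A second objection is that the planned covariates may already absorb part of what prior cost predicts. That is right, and is why ρ must be the correlation remaining after them; a raw pre/post correlation could overstate the gain.

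Third, this is a secondary endpoint with no power target, and nothing here makes the planned comparison invalid. That also stands.

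**Conclusion.** The point holds as one of precision on a secondary endpoint. The variance cut of about 9% to 49% rests wholly on an assumed residual correlation of 0.3 to 0.7, a linear scale and complete pre-index claims.

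Two stronger readings are tempting, and the documents support neither.

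- A reader might infer that the cost estimate is biased because prior spending is left unadjusted. Allocation is by patient, 1:1 and computer-generated, so any imbalance in prior spending is chance, which the standard error already reflects.
- A reader might infer from the phrase "The marginal effect of being assigned to an intervention clinic" that the cost effect is undefined or a clinic-level contrast. The sentence before it estimates costs by study arm, section 9.4 makes the patient's randomized arm the primary predictor, and H2.1 compares subjects by assignment. The phrase appears to be left over from the abandoned cluster design, as does similar wording in section 10.1.9.1. It needs correcting but is unlikely to mislead the analyst.

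**What to change.** In section 9.4.3, with matching wording in H2.1:

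1. State that the outcome is post-index cost, and pre-specify 12-month pre-index cost as a covariate in the gamma/log-link model: log cost, with a zero-cost indicator. If a repeated-measures model is intended instead, write out its terms and do not also enter pre-index cost as a covariate.
2. Build the covariate in the same TCRRV units and service categories as the outcome. If emergency and inpatient costs are left out of one, leave them out of the other.
3. Annualize pre-index cost for patients with partial pre-index coverage, and use a separate indicator for absent coverage. A zero-cost indicator alone would mix patients who spent nothing with patients whose spending was not observed.
4. Reconcile the coverage rules in sections 5.2 and 9.3 so that the cost population is defined once.
5. Editorially, name the effect as the marginal effect of the patient's randomized arm.

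The cost is small: a revision of the analysis plan, a few model terms, and programming to handle incomplete pre-index claims. The plan already calls for costs from the pre-index period, so no new data source is needed.

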The study population will be simulated at the patient level by assigning the known characteristics of the adherence intervention and control groups to synthetic counterparts. Age, sex, race/ethnicity, BMI, systolic BP, cholesterol, smoking status, CV disease history, diabetes status, A1C, and medication use for persons in each study group at the end of the study follow-up period will be entered into the model baseline. Linear, exponential, logarithmic and, if appropriate, polynomial trends, will be fit to the observed intervention differences in medication adherence, CV risk factors, and A1C (identified by H1.1-H.3 and secondary analyses) and used to project future differential trends between the simulated ReachOut adherence intervention and control groups. Incidence of major CV events will be determined using risk equations developed specifically for the model using Framingham Heart Study data.^{130,131} Calculation and reporting of incremental cost-effectiveness ratios (ICERs) will follow the guidelines of the Panel on Cost-Effectiveness in Health and Medicine.¹³² ICERs will be estimated with a 30-year analytic horizon in the primary analysis, and 10- and 20-year horizons will be considered in secondary analyses. Sources of uncertainty will be evaluated using standard sensitivity methods.¹³³

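### The 30-year microsimulation starts each arm from its own patients, so chance arm differences in age, sex, race/ethnicity and pre-index CV history count toward the incremental events, costs and ICER

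*Combined protocol and SAP*

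**What the plan says.** Section 9.4.3 (Analytic Plan for Long-term Costs and Outcomes) simulates the study population at patient level "by assigning the known characteristics of the adherence intervention and control groups to synthetic counterparts". The inputs are listed together: "Age, sex, race/ethnicity, BMI, systolic BP, cholesterol, smoking status, CV disease history, diabetes status, A1C, and medication use". The same sentence fixes whose values these are and when they are taken: those "for persons in each study group at the end of the study follow-up period will be entered into the model baseline".

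Trends are then fitted to the observed intervention differences in adherence, CV risk factors and A1C, and are "used to project future differential trends between the simulated ReachOut adherence intervention and control groups". Major CV events come from risk equations developed for the model. On the horizon, the section says that "ICERs will be estimated with a 30-year analytic horizon in the primary analysis". On uncertainty it says: "Sources of uncertainty will be evaluated using standard sensitivity methods", with a reference.

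H2.2 in Section 9.1 rests on this simulation. It posits that patients assigned to the intervention will have "significantly lower overall resource use and fewer major CV and diabetes-related events" over a simulated 30 years after the intervention.

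Two other parts of the plan treat arm differences in patient characteristics explicitly. The Aim 1 models in Section 9.4.2 screen characteristics and include those found unbalanced by arm. The 12-month cost model in Section 9.4.3 "will be used to estimate costs by study arm while controlling for demographics and baseline clinical risk factors".

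**The concern.** A cost-effectiveness comparison should ask what happens to the same people under two strategies. As written, the model compares two different groups of people. Some listed inputs can respond to the intervention (SBP, cholesterol, A1C, medication use). Others cannot: age, sex, race/ethnicity, and whatever part of CV disease history was present before the index visit. If one arm happens to be older or to include more patients with prior CV disease, its simulated events and costs will differ for that reason alone, and the difference is credited or charged to the intervention.

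The estimated trial differences do not correct this. In the text they shape the future trends between arms; they are not said to replace the arm-specific starting values. A long horizon gives any difference in starting age or disease history many annual cycles in which to act. The ICER and the H2.2 conclusion are at stake.

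**Working it through.** **What is stated for each analysis**

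| Analysis | Section | Handling of chance arm differences |
|---|---|---|
| Aim 1 adherence, SBP, A1C | 9.4.2 | Unbalanced characteristics are screened and added to the model |
| 12-month costs (H2.1) | 9.4.3 | Demographics and baseline clinical risk factors controlled |
| 30-year simulation (H2.2) | 9.4.3 | None stated: no common cohort, matching, reweighting or adjustment |

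Section 6.3 gives 1:1 computer-generated allocation and mentions no stratification, so the design is not stated to balance these traits beyond what chance provides.

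**Size of a simulated arm.** The plan gives no number for the simulation, so I take it from Section 9.2. The halved cohort sizes reproduce: 2,132/2 = 1,066 (BP), 1,664/2 = 832 (glycemia), 3,388/2 = 1,694 (statin). Patients can qualify for more than one cohort, and the overlap is not given. The bounds are:

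- Full overlap with the statin cohort: 1,694/2 = 847 per arm.
- No overlap: (1,066 + 832 + 1,694)/2 = 3,592/2 = 1,796 per arm.

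**Chance difference between arms, 95% range.** For a mean it is 1.96 × SD × √(2/n). For a proportion it is 1.96 × √(2p(1−p)/n). Here n is the number per arm. The age SD, the share with CV history and the sex split are assumptions, because the documents give none of them.

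| Trait and assumption | 847 per arm | 1,796 per arm |
|---|---|---|
| Age, SD 8 | ±0.76 years | ±0.52 years |
| Age, SD 10 | ±0.95 years | ±0.65 years |
| Age, SD 12 | ±1.14 years | ±0.78 years |
| CV history 10% | ±2.9 points | ±2.0 points |
| CV history 20% | ±3.8 points | ±2.6 points |
| CV history 30% | ±4.4 points | ±3.0 points |
| Sex, 50% | ±4.8 points | ±3.3 points |

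The extremes, written out:

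- Age, high: 1.96 × 12 × √(2/847) = 1.14. Age, low: 1.96 × 8 × √(2/1,796) = 0.52.
- CV history, high: 1.96 × √(0.42/847) = 0.044. CV history, low: 1.96 × √(0.18/1,796) = 0.020.

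If both strategies are run on one common cohort, all of these differences are exactly zero.

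I do not convert these ranges into events or dollars. The coefficients of the risk equations are not in the documents, so the step from years of age to ICER would rest on outside figures.

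**The case against.** The strongest reply is that randomization already deals with this. The expected difference in every fixed trait is zero, the endpoint is secondary, and the plan promises sensitivity analysis with a reference on parameter estimation and uncertainty. The enrolment figures are also deliberately halved for the pandemic. If the full numbers arrived, every range above would be divided by √2, giving about ±0.4 to 0.8 years and ±1.4 to 3.1 points. All of that is right, and it limits the point to precision. It does not remove it: resampling patients would reveal the noise, whereas a common cohort would eliminate the part due to fixed traits.

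A reader might infer more than the documents support:

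- *That the ICER is biased.* It is not, in expectation. The distortion is whatever chance produces in this one trial.
- *That the simulation has no valid error statement.* Uncertainty methods are named and referenced. The fair criticism is that they are generic and not tied to H2.2.
- *That significance would depend on how many persons are simulated.* No test across simulated persons is described, and no number to be simulated is given. The supportable point is that no criterion is stated for the word *significantly* in H2.2.
- *That patients lost before the end are left out.* Section 7.3 includes all eligible patients except research opt-outs and says that those without follow-up are handled in the analysis. The Schedule of Activities runs the algorithms outside encounters on all study-eligible patients. Only deaths, anticipated at under 2%, are clearly absent at the end.
- *That every arm difference in CV history is chance.* It is taken at the end of follow-up, so events since the index visit may reflect a real effect. Only the pre-index part is fixed.
- *That SBP differences show the same fault.* SBP is modifiable, and most of its chance variation is ordinary sampling error of the trial effect, which any sound method retains.
- *That the single-condition cohorts set the scale.* The simulation is of the study population, so the larger arms above apply.

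**Conclusion.** The point holds as a matter of method and precision. As written, the 30-year comparison includes chance differences in traits that the intervention cannot alter, and it is the only one of the three analyses compared above with no stated step to deal with them. For arms of 847 to 1,796 patients, the 95% chance range is about ±0.5 to 1.1 years of mean age and ±2.0 to 4.4 percentage points of CV history.

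This rests on the assumed age SD (8 to 12 years), the assumed prevalence (10 to 30%), the unknown cohort overlap and the halved enrolment. It also assumes that the model uses these traits to predict events, which is the evident reason for entering them. The effect on the ICER itself cannot be sized from the documents. The team may intend a common cohort, but the text describes arm-specific ones.

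**What to change.** Amend Section 9.4.3 as follows.

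1. Build one pooled synthetic cohort from all randomized patients and run it under both strategies, with identical age, sex, race/ethnicity and pre-index CV history.
2. Keep the start after the intervention period and the 30-year horizon. H2.2 is framed as post-intervention, and pooling does not require moving the start to the index visit.
3. Let the strategies differ only by the covariate-adjusted trial effects on SBP, A1C, other modifiable risk factors and adherence. State how CV events between the index visit and the model start are handled, since these may be a real effect.
4. Draw those effects from their estimated sampling distribution, or bootstrap the trial, and carry the draws through the model.
5. Define *significantly* in H2.2 by the resulting 95% uncertainty interval for incremental resource use and events.

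The cost is a change of model inputs, some SAP wording and extra simulation runs. No new data are needed.
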